Hypothesis 1.1: Bladder instillation with a gentamicin antimicrobial solution will result in significantly decreased episodes of symptomatic UTIs, fewer courses of oral antibiotics, and a reduction of multi-drug resistant organisms on urine culture, as compared to controls.

Hypothesis 1.2: Bladder instillation with a gentamicin antimicrobial solution will decrease detrusor spasms, increase bladder compliance as well as mitigate the rapid rise in systolic blood pressure (autonomic dysreflexia) evidenced during cystometry as compared to controls.

B. Study Design/Methodology

In a randomized, double-blind, prospective study, we will compare the long-term effects (80 daily sessions, 2x per day) of a bladder instillation protocol in 3 groups of individuals (n=36; 3 groups of 12) with chronic SCI receiving either:

1) gentamicin bladder instillation

2) saline installation

3) no instillation (catheter clamping only in those with suprapubic catheters for the duration of the irrigation time frame - refer to Fig. 2 timeline).

The control groups will also serve to address the question of whether bacteria already colonized in the bladder would also provide a protective role in preventing more pathogenic bacteria or other organisms, such as yeast, which also colonize the bladder. Research participants will complete the 80 sessions of twice per day instillations initially in the Urogenital and Bowel Laboratory, where blood pressure and heart rate will be continually monitored (approximately 1-2 weeks). Once safe pressures are established, the remaining instillations may be completed in the home setting. A major issue confounding validity of a clinical trial is compliance. Given that this study assesses the long-term outcomes of daily bladder instillations and allows for the twice-daily instillations to be conducted in the home-setting, it is possible that participants may not be fully

compliant with respect to study duration and frequency of instillations. In an effort to improve the applicability of the study results to individual participants and mitigate non-compliance, our research nurse will guide participants through all aspects of the instillation procedure to ensure that they are fully independent. At-home blood pressure monitoring during instillation times is automatically recorded and will be an additional step in monitoring protocol adherence.

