Gentamicin sulfate will be prescribed for the research participants by the study physician or nurse practitioner. A formulation derived from 480 mg gentamicin sulfate diluted in 1 L normal saline will be used for instillation. The formulation will be prepared by the pharmacy, located at the study site (first floor of Jewish Hospital), in a laminar flow hood using USP 797 regulations just prior to the scheduled assessment (within 20-30 minutes) and stored in the refrigerator at a temperature range of 2-8°C until use in the outpatient setting. Gentamicin will be compounded for immediate use in single-dose, disposable BD 50ml Luer-Lok tip syringes. The container closure system for the diluted gentamicin sulfate solution is sterile and depyrogenated. A 60 ml syringe containing the gentamicin solution will be connected to the end of the catheter through which the solution will be slowly infused over 1-2 minutes (depending on bladder capacity – determined from initial Urodynamics) after drainage of urine is complete. The solution will remain in the participant's bladder for a least 30 minutes (unless the participant is experiencing autonomic dysreflexia, and in that case, immediately drained) with the goal of attaining 2 hours.

Participants will undergo initial instillations in the laboratory to determine the optimal bladder instillation storage time frame while monitoring blood pressure throughout the intervention. The initial intervention

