sessions will be performed in the laboratory. The time frame to retain the instillation treatment in the bladder will be incrementally increased by 15 minute intervals in the laboratory over the course of 3 - 4 weeks. Instillation retention times may begin for 30 minutes. Once 3 consecutive days of stable blood pressure values without autonomic dysreflexia are demonstrated during that time frame, the time will be increased to 45 minutes and the same process will continue by 15 minute intervals, up to 2 hours, as long as blood pressure remains stable throughout the instillation retention time frame. The instillation retention time frame will not be increased if the participant experiences autonomic dysreflexia and thus, an optimal time frame in which his/her blood pressure remains stable during the intervention will be established. Once 3 consecutive stable days are achieved with the same instillation parameters and the participant has demonstrated self-sufficient use of the instillation procedure, he/she will be sent home for one day to perform the twice daily instillations at home. For home instillations, the participant will be instructed and provided with written instructions indicating that the solution is to be stored in the refrigerator no more than 10 days and stored at room temperature for no more than 48 hours. The participant will return to the laboratory the following day for instillation with blood pressure monitoring. Provided blood pressure parameters remain stable, the participant will be allowed to complete the intervention at home for 3 days prior to returning to the laboratory for instillation and blood pressure monitoring. If blood pressure parameters remain stable, the participant will be able to begin the home intervention program of 6 days a week and 1 day in the lab. Participants will be instructed to monitor blood pressure for at least 15 minutes.

2. Saline Instillation

A 50ml syringe containing saline will be connected to the end of the catheter and slowly infused over 1-2 minutes after drainage of urine is complete. The saline will remain in the participant's bladder for at least 30 minutes (unless the participant is experiencing autonomic dysreflexia, and in that case, immediately drained) with the goal of attaining 2 hours. Note that participants will follow the same instillation training paradigm as mentioned above, including the incremental progression of instillation retention time with stable blood pressure values.

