3. Bladder Clamping Protocol – no instillation (for those with suprapubic catheters)

Participants with suprapubic catheters will be instructed by the research urology nurse on how to perform a catheter clamping protocol. These procedures will initially be conducted in the laboratory setting until the participant can demonstrate independence with clamping and blood pressure remains stable during that time frame. To begin, the nurse will instruct the participant on how to slide the plastic piece of the suprapubic tube to the "closed" position and plug the end of the tube. This will ensure that urine is not draining from the tube. After the tube has been clamped for 15 minutes, the participant will un-clamp the suprapubic tube, take the plug off the end, and draining any additional urine into a collecting "hat" or urinal. What comes out of the suprapubic tube will be measured. The nurse will record this amount on a chart as a measurement of the participant's bladder capacity. This procedure will be repeated 4 times a day until he/she can work up to clamping for 30 minutes, increased by 15 minute intervals, up to 2 hours as indicated above in the instillation description (if appropriate). Each day the nurse will help the participant re-clamp the tube, plug the end, and continue recording residual urine that comes out of the tube. At night, the participant may keep the suprapubic tube connected to a bag in order to let the bladder drain during sleep. When the participant is able to demonstrate independence with clamping, he/she will restart bladder clamping in the home setting, clamping the suprapubic catheter 4 times a day for up to 2 hours each time. He/she will continue to clamp the suprapubic tube throughout the duration of this study.

4. Urine Sample Collection and Culture

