Day-to-day oversight of the trial is provided by the Principal Investigators (PIs), Drs. [name] and [name]. They will review all study data and any adverse events, and report all adverse events to the Medical Monitor, sponsor, and University of Louisville IRB. Monitoring for the study will be provided by a Medical Monitor who will review study conduct including accrual, drop-outs, protocol deviations, and AEs in aggregate on an annual basis. The Medical Monitor will review serious adverse events (SAEs) in real-time. All data analyses (Labs, urodynamics, ultrasound) will be conducted as assessed with annual summary reports generated. Study data will be provided to the Medical Monitor to each annual review

one month prior. Data reports will be prepared by the principal investigators and the study statistician. The Medical Monitor will provide a written report to the study team with recommendations for study modification, study continuation/discontinuation as relevant. The study team is responsible for forwarding the report to the IRB.

Figure 2. Study Timeline.

Screening Phase		Intervention		Midpoint		Intervention			Post Intervention		
Assessments		Groups		Assessments		Groups			Assessments		
Labs	*Fxnl	Gent (n=12)	Saline (n=12)	None (n=12)	Labs	*Fxnl	Gent (n=12)	Saline (n=12)	None (n=12)	Labs	*Fxnl
UA Culture + Sensitivity	UDS US ~Intake forms	IC (n=6) 28.8 mg in 60 ml NS	IC (n=6) 60 ml NS	IC (n=6) No procedure	UA Culture + Sensitivity CBC CMP HCG	UDS US ~Intake forms	IC (n=6) 28.8 mg in 60 ml NS	IC (n=6) 60 ml NS	IC (n=6) No procedure SP (n=6) Catheter clamping for duration of instillation.	UA Culture + Sensitivity	UDS US ~Intake forms
CBC CMP HCG		SP (n=6) 28.8 mg in 60 ml NS	SP (n=6) 60 ml NS	SP (n=6) Catheter clamping for duration of instillation			SP (n=6) 28.8 mg in 60 ml NS	SP (n=6) 60 ml NS		CBC CMP HCG	
5 days		80 instillations - 7x/wk - 2x/d		5 days		80 instillations 7x/week – 2/d			5 days		

CBC, Complete Blood Count; CMP, Comprehensive Metabolic Panel; Gent, Gentamicin sulfate; IC, Intermittent Catheterization; Fxnl, Functional; HCG, Human Chorionic Gonadotropin (Pregnancy Test); NS, Normal Saline; SP, Suprapubic Catheter; UDS, Urodynamic Study; US, Ultrasound.

*The term "functional", abbreviated fxnl in this study, signifies an objective assessment of bladder functioning using urodynamic testing and ultrasound imaging.

IV. References

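### Suprapubic no-instillation controls clamp four times a day in one section, while the study design and Figure 2 tie clamping to a twice-daily dwell; the difference is not explained

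*Combined protocol and SAP*

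**What the plan says.** **Bladder Clamping Protocol (Research Procedures, item 3).** A frequency of four a day appears twice. For laboratory training: "This procedure will be repeated 4 times a day until he/she can work up to clamping for 30 minutes". For home: "clamping the suprapubic catheter 4 times a day for up to 2 hours each time", continuing for the rest of the study. The first clamping lasts 15 minutes, and the length then rises in 15-minute steps to 2 hours if appropriate, with a reference back to the instillation description.

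**Study Design/Methodology (II.B).** The protocol is described as "80 daily sessions, 2x per day) of a bladder instillation protocol in 3 groups of individuals". The third group is defined as "catheter clamping only in those with suprapubic catheters for the duration of the irrigation time frame", with a pointer to Figure 2.

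**Figure 2, Study Timeline.** The suprapubic cell of the no-instillation group (n=6) reads "Catheter clamping for duration of instillation". The timing row of that block reads "80 instillations - 7x/wk - 2x/d". The intermittent-catheterization half of the group (n=6) has no procedure.

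**Instillation arms (Research Procedures, items 1 and 2).** Participants "perform the twice daily instillations at home". Retention is at least 30 minutes, "with the goal of attaining 2 hours", and may start at 30 minutes. The saline arm follows the same training progression as the gentamicin arm.

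No section gives a reason for a clamping frequency that differs from the instillation frequency.

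**The concern.** Clamping appears to be there so that suprapubic controls store urine over the same periods in which the other arms hold fluid. It does that job only if the schedules match.

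The protocol itself treats bladder storage as active. Specific Aim 1 lists over-distention among the risk factors for UTI. The background section says distention can provoke autonomic dysreflexia in people injured at T6 or above. The risk section rates marked heart rate or blood pressure changes from clamping or urodynamics as likely. Hypothesis 1.2 then compares detrusor spasms, compliance and the blood pressure rise during cystometry with controls.

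If half of the no-instillation arm stores urine more often than the other arms dwell, a gentamicin versus no-instillation difference in those outcomes could partly reflect the clamping schedule. There is also a practical risk: staff working from different sections could give participants different instructions.

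**Working it through.** **1. The plan's own figure for this control arm.** The Statistical Plan states 96% power for gentamicin versus no instillation on symptomatic UTIs, with n = 12 per arm, a difference of 2, SDs of 1.7 and 0, and a two-sided unequal-variance t-test at 0.05.
- Standard error = √(1.7²/12 + 0²/12) = 0.491
- Noncentrality = 2/0.491 = 4.08
- Welch–Satterthwaite df = 11
- Power = 0.959, which matches the stated 96%

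Clamping frequency does not enter this calculation, so the figure stands whichever schedule applies.

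**2. Storage periods per day.** Suprapubic control under the clamping section: 4. Instillation arms: 2. Ratio 4/2 = 2. Over the 80 days given under Screening and Enrollment, this is 4 × 80 = 320 clampings against 2 × 80 = 160 dwells. Within one Figure 2 block (80 instillations at 2 a day = 40 days), it is 160 against 80.

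**3. Storage time per day.** Let c be the length of one clamping and d the length of one dwell. Clamped time is 4c, dwell time is 2d, and the ratio is 4c/2d = 2c/d.

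| Situation | 4c | 2d | Ratio |
|---|---|---|---|
| Starting values (c = 15 min, d = 30 min) | 60 min | 60 min | 1.0 |
| Both at 30 min | 2 h | 1 h | 2.0 |
| Both at the 2 h ceiling | 8 h | 4 h | 2.0 |

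The ratio is 2 whenever c = d, and 1 when each clamping is half as long as each dwell.

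**4. How soon the ceiling can be reached.** In the instillation arms, going from 30 to 120 minutes takes (120 − 30)/15 = 6 steps. Each step needs 3 consecutive stable days, so at least 18 days pass first. Retention time is not increased if autonomic dysreflexia occurs, so some participants may never get there.

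**5. The two readings of duration.**
- *It covers frequency as well as length.* Study Design and Figure 2 then imply clamping twice a day, and the clamping section says four times. The sections conflict.
- *It covers length only.* Study Design and Figure 2 set how long each clamping lasts, and the clamping section sets how often. All three can be followed, but the control then has twice as many storage periods a day as the other arms, unexplained.

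Both readings leave something to correct.

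**The case against.** The strongest reply is that no section says in words to clamp twice a day. In Study Design, the twice-daily figure qualifies an instillation protocol. In Figure 2, it counts instillations, which this arm does not receive, and the extracted table leaves the span of that row uncertain. The clamping section itself ties clamp length to the instillation description. This stands, to the extent that an outright contradiction is not proven. Against it, Study Design applies its frequency to three groups, and the length-only reading does not remove the unexplained difference of 4 against 2.

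A reader might also infer that the control receives double the bladder filling on every day of the study. The documents do not support that. Clamped time equals dwell time at the starting values, and the 2-hour figure is an upper limit in all arms. Hours are also not volume: the instillation arms hold about 50–60 ml of added fluid plus urine, the clamped controls hold urine only, and no urine volumes are given.

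The scope is limited as well. Six of 36 participants are affected, in an arm that is not blinded and that the Blinding Plan calls standard of care, within a self-described feasibility study. No analysis by catheter type is planned, so there is no suprapubic-only contrast to protect. These points restrict the size of the problem. They do not restore the match between clamping and dwell.

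**Conclusion.** The point holds as an unreconciled clamping schedule. Followed as written, the clamping section gives 6 of the 12 no-instillation participants 4 storage periods a day against 2 in the instillation arms. Daily storage time ranges from equal (60 minutes each, at the starting lengths) to double (at any equal session length, up to 8 h against 4 h). Whether this is a direct contradiction depends on whether duration is meant to include frequency.

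A difference in storage schedule can bias the Hypothesis 1.2 comparisons with the no-instillation arm. Neither the size nor the direction of any bias can be worked out from the documents, and over-distention in the control is not shown. The 96% power figure is unaffected.

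**What to change.** Reconcile Study Design/Methodology, the Bladder Clamping Protocol section and Figure 2 so that all three state one clamping frequency and one duration per clamping. Which schedule to adopt is for the investigators; this review does not choose.

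If the adopted schedule still differs from the dwell schedule, state the difference and the reason for it. In that case, attribute urodynamic and blood pressure effects under Hypothesis 1.2 to gentamicin only through gentamicin versus saline, whose arms share one schedule. Report gentamicin versus no instillation as a comparison of the whole regimens. The Statistical Plan already contains the gentamicin versus saline test, as a pairwise follow-up to a significant three-group ANOVA.

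The cost is protocol wording, participant instructions and a narrower claim from the no-instillation comparison. No extra participants or procedures are needed. The plan states power only for symptomatic UTIs, so no stated power for the Hypothesis 1.2 outcomes is given up.

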Urine collected for cultures will be collected as a clean-catch midstream technique from an immediately installed urine catheter or as a suprapubic aspiration from an installed catheter (52). For participants having a suprapubic catheter, the catheter will be clamped for 20 to 30 minutes until at least 5 mL of urine can be collected. The catheter will then be unclamped, and urine will be allowed to flow into a sterile plastic container. In those that use intermittent catheterization, participants will be required to first cleanse the urethral area with a castile soap towelette. A sterile 12 French straight catheter is inserted through the urethra into the bladder. The first portion of the urine stream should flow into the toilet in order to reduce the opportunities for contaminants to enter into the urine stream. The urine midstream is then collected into a clean container (any excess urine will be emptied into the toilet), Urine samples will be placed in

sterile storage vials and stored at 4C for less than 3 hours and sent to the Outpatient Care Center, Jewish Hospital for analysis. Symptomatic UTIs will be defined as a participant complaint of symptoms consistent with UTI (cloudy/foul smelling urine, fever, chills, increase in bladder and/or lower extremity spasms, worsening dysreflexia, leakage, or pain) combined with a positive leucocyte esterase and/or nitrates on dipstick urinalysis or a urine microscopy with > 10 WBC/HPF (white blood cells/high powered field) with a urine culture with >10⁵ bacteria/ml (46). Note that urine smell and cloudiness alone (i.e. without other symptoms) are not considered UTI signs, given their high prevalence in this catheterizing population. All cultured microorganisms will be identified to the species level and quantified as colony-forming units per ml (cfu/ml⁻¹) (16). If the microorganism(s) cultured is/are resistant to three or more different antimicrobial agents to which the microorganism would normally be susceptible, it will be defined as being multi-resistant. If a participant is diagnosed having a symptomatic UTI necessitating systemic antibiotics by the study physician/nurse practitioner, he/she will follow standard of care treatment under provider oversight. The study physician/nurse practitioner will recommend whether or not continuation of either the instillation or clamping protocol is appropriate for the participant during systemic antibiotic treatment.

5. Blood Draw

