University of Louisville Hospital and Frazier Rehab Institute evaluates approximately 300 chronic SCI outpatients each year. We also have a database of over 5,000 people with SCI who have expressed interest in participating in our research programs. We will select individuals to assure that there is a minimum of 25% women to adequately represent the percentage in the SCI population.

All SCI research participants, irrespective of gender, will be selected based on the following:

Inclusion Criteria

- At least 18 years of age;
- Non-progressive spinal cord injury;
- Stable medical condition;
- Bladder dysfunction as a result of spinal cord injury
- History of recurrent UTIs (defined as 3 or more within the past year or 2 or more within the past 6 months).

Exclusion Criteria

- Signs or symptoms of serious UTI that requires the use of systemic antibiotics;
- Use of any urine-acidifying agent, bladder irrigant, or systemic antibiotic within the previous 2 weeks;
- Participants colonized with gentamicin-resistant bacteria on baseline urine culture or a gentamicin allergy/sensitivity;
- Participants with known hearing loss and/or renal disease;
- Pregnant at the time of enrollment or planning to become pregnant during the time course of the study.

A. Screening and Enrollment

Potential research participants will be identified by our research database (UofL IRB 06.0647) and contacted by research staff prioritized by the initial date they entered the database and provided with general information regarding the research study. If the individual is interested in learning more about the study, the clinical coordinator will set up an info session via teleconference or a meeting at Frazier Rehab Institute. The designated project leader and clinical coordinator will attend the info session and the project leaders (Drs. [name] and [name]) will describe the project including the time commitment, the general design of the study, the interventions and the randomization process. Specific questions from the potential research participant will be answered.

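### No stated rule separates urine cultures from a gentamicin dwell, so symptom-triggered specimens could carry drug in one arm only

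*Combined protocol and SAP*

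**What the plan says.** **Sampling.** For suprapubic users, Urine Sample Collection and Culture says "the catheter will be clamped for 20 to 30 minutes until at least 5 mL of urine can be collected". For intermittent-catheter users, "The first portion of the urine stream should flow into the toilet in order to reduce the opportunities for contaminants", a discard aimed at contaminants. Specimens are "stored at 4C for less than 3 hours and sent to the Outpatient Care Center". The section sets no minimum time since the last instillation, no pre-dose rule, no neutralising step and no recording of time since dose.

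**Exposure.** Intravesical Gentamicin Sulfate Instillation states: "A formulation derived from 480 mg gentamicin sulfate diluted in 1 L normal saline will be used for instillation". On the dwell: "The solution will remain in the participant's bladder for a least 30 minutes", with 2 hours as the goal. Figure 2 (Study Timeline) gives "28.8 mg in 60 ml NS" and shows instillations twice a day, seven days a week.

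**Partial separation.** Figure 2 lists culture and sensitivity only in the screening, midpoint and post-intervention columns. Each is a 5-day block drawn apart from the instillation columns. The Urodynamics section asks participants to stop bladder medications for 24 hours beforehand and allows that urine to be cultured. Neither place says whether study instillations stop.

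**Use of the cultures.** Specific Aim 1 lists bacterial number, species and resistance as outcomes. Hypothesis 1.1 covers symptomatic UTIs and multi-drug resistant organisms. The UTI definition combines symptoms with a positive dipstick or microscopy above 10 WBC/HPF, then adds a culture above 10^5/ml. It is unclear whether that last condition attaches to both routes or only to microscopy.

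**Entry.** The exclusions cover "Participants colonized with gentamicin-resistant bacteria on baseline urine culture" and any bladder irrigant or systemic antibiotic in the previous 2 weeks.

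**The concern.** During treatment a symptomatic participant is seldom more than some hours from a dwell, and no rule places the specimen before the next dose rather than after the last one. Any gentamicin left in the bladder would enter the specimen and could suppress growth there, whatever is happening in the participant.

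The effect would run one way. In the saline arm a recent dwell can only dilute the urine, and the no-instillation arm has nothing to carry over. Baseline cultures are protected by the 2-week irrigant exclusion, and on-treatment cultures have no stated equivalent. Both the paired pre-post comparison within the gentamicin arm and the between-arm comparison in the Statistical Plan could therefore be affected. Selective loss of susceptible organisms could also distort the species and resistance results.

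**Working it through.** **Step 1. Instilled concentration.** 480 mg in 1 L is 480 µg/ml. Figure 2 gives 28.8 mg / 60 ml = 0.48 mg/ml = 480 µg/ml. The two agree.

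**Step 2. Carry-over, instillate undiluted.** With r ml left after drainage and u ml of fresh urine, concentration = 480 × r/(r + u). The 5 ml minimum and the 20 to 30 minute clamp are in the plan. The values of r and the other values of u are assumptions.

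| r (ml) | u (ml) | Calculation | µg/ml |
|---|---|---|---|
| 0.5 | 30 | 480 × 0.5/30.5 | 7.9 |
| 2 | 5 | 480 × 2/7 | 137 |
| 0.5 | 300 | 480 × 0.5/300.5 | 0.8 |
| 2 | 300 | 480 × 2/302 | 3.2 |

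**Step 3. Dilution during the dwell.** At an assumed inflow of 1 ml/min, a 60 ml instillate falls to 480 × 60/(60 + 30) = 320 µg/ml after 30 minutes and 480 × 60/(60 + 120) = 160 µg/ml after 2 hours. The Step 2 figures then drop by a factor of 1.5 or 3. The same inflow would yield 20 to 30 ml during the clamp, so the internally consistent range at 1 ml/min is:
- 30-minute dwell: 320 × 0.5/30.5 = 5.2 to 320 × 2/22 = 29 µg/ml
- 2-hour dwell: 160 × 0.5/30.5 = 2.6 to 160 × 2/22 = 14.5 µg/ml

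The 137 µg/ml end requires a slow inflow, 5 ml in 20 to 30 minutes.

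**Step 4. Larger residuals.** Aim 1 names large post-void residuals as a risk factor in this population. With r = 1 to 20 ml and 25 ml of fresh urine, a suprapubic specimen holds 320 × 1/26 = 12 to 320 × 20/45 = 142 µg/ml after a 30-minute dwell, or 160 × 1/26 = 6 to 160 × 20/45 = 71 µg/ml after 2 hours. An intermittent-catheter specimen at the first later emptying (2-hour dwell, residual 5 to 50 ml, emptied volume 300 to 400 ml) holds 160 × 5/400 = 2 to 160 × 50/300 = 27 µg/ml. By the third later emptying the highest value is 160 × (50/300)^3 = 0.7 µg/ml. Carry-over is therefore a matter of hours after a dwell, not days.

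**Step 5. What a one-sided loss would do (illustration only).** The planned between-arm power reproduces: difference 2, SD 1.7 against SD 0, n = 12 per arm, noncentral t with 11 df and noncentrality 2/(1.7/√12), gives 95.9% (stated 96%). Now suppose no true drug effect, an assumed 2 to 4 UTIs per 6 months, and a share f of episodes masked in the gentamicin arm only. The spurious difference is f × 2 to f × 4.

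| f | Spurious difference | Rejection, control SD 0 | Rejection, SD 1.7 in both arms |
|---|---|---|---|
| 0.10 | 0.2 to 0.4 | 7 to 12% | 6 to 9% |
| 0.25 | 0.5 to 1.0 | 15 to 46% | 11 to 28% |

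The nominal level is 5%. Nothing in the documents fixes f, and it could be zero.

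**The case against.** A reader might infer that nothing keeps cultures away from dosing, that the bacteriuria outcomes are biased, and that the trial would record carry-over as efficacy. The documents do not support that much.

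- **Scheduled cultures are probably apart from dosing.** Figure 2 draws them in separate blocks, and Screening and Enrollment describes the final assessments as following the protocol. This stands as a likely safeguard, although no pause or gap is stated. The weekly laboratory day is described for instillation and blood pressure monitoring, and no culture is scheduled on it.
- **The UTI count may not depend on culture.** If symptoms plus a positive dipstick are enough, a suppressed culture loses no episode counted by that route. This stands until the definition is clarified. The species, count and resistance results depend on culture either way.
- **Organisms are not susceptible by design throughout.** Resistance is screened at baseline only. The risk list includes growth of gentamicin-resistant organisms, and the background limits the drug's activity primarily to Gram-negative aerobes and facultative anaerobic bacilli. This stands: later infections may be unaffected by carried-over drug.
- **The concentrations do not show lost growth.** Residual volume and inflow are assumed, and the documents give no inhibitory concentration or plating method. This also stands.

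None of these points supplies a rule for symptom-triggered cultures taken between twice-daily doses.

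**Conclusion.** The gap is real but narrow. No stated rule separates a culture from a dwell, and the exposed specimens are mainly the symptom-triggered ones during the dosing blocks. Scheduled cultures are exposed only if instillations continue through the 5-day blocks. The high concentrations apply to suprapubic specimens taken straight after drainage. They shrink quickly with fresh urine and depend throughout on the assumed residual and inflow. An effect on UTI counts further requires that culture be mandatory in the definition. Bias in favour of gentamicin is possible, not demonstrated, and its size cannot be derived from the documents. Because it could run only one way, and could not be examined afterwards without a recorded time since dose, a cheap correction is worthwhile.

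**What to change.** In Urine Sample Collection and Culture:

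1. State that on-treatment cultures in the two instillation arms are taken, where possible, from the urine drained just before an instillation. In the no-instillation arm, where intermittent-catheter users have no procedure, take scheduled cultures at a comparable time of day.
2. Record time since the last instillation for every culture.
3. Do not delay urgent symptom-triggered samples. Flag those taken soon after a dwell, using a cut-off fixed in advance, and keep the episode in the main analysis.
4. Add a sensitivity analysis that classifies flagged episodes by symptoms plus dipstick or microscopy, without relying on the culture count. No episode is dropped.
5. State whether study instillations pause in the 5-day assessment blocks, and whether culture is required on the dipstick route of the UTI definition.

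The cost is one more recorded time, two clarifying statements and a small sensitivity analysis. Sample size and visit schedule do not change.
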